7.5. Electrocardiogram Results

A shift table of the Investigators' assessment of ECG results at each visit compared with baseline values will be presented by treatment group using the following categories:

- normal

- abnormal (not clinically significant)
- abnormal (clinically significant)
- missing/not done

The number and percentage of subjects in each cross-classification group of the shift table will be presented. Subjects with a missing value at Baseline or postbaseline will not be included in the denominator for percentage calculation.

A by-subject listing for ECG assessment results will be provided by subject ID number and visit in chronological order.

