5.3 Exclusion Criteria

Subjects who meet **any** of the following exclusion criteria will not be eligible for the study:

1. Prior treatment for CHB; specifically
 - a. lamivudine, telbivudine or adefovir (any duration)
 - b. NrtI treatment for >4 weeks
 - c. HBV core inhibitors (any duration)
 - d. Previous treatment with an investigational agent for HBV infection
2. Co-infection with human immunodeficiency virus (HIV), hepatitis C virus (HCV), hepatitis E virus (HEV), or hepatitis D virus (HDV)
3. Females who are lactating, or wish to become pregnant during the course of the study
4. History or evidence of advanced liver disease or hepatic decompensation (including jaundice, ascites, portal hypertension, gastrointestinal bleeding, esophageal varices, hepatic encephalopathy) at any time prior to, or at the time of Screening
5. History of persistent alcohol abuse (alcohol consumption exceeding 2 standard drinks per day on average [1 standard drink = 10 grams of alcohol]) or illicit drug abuse within 3 years of Screening
6. Clinically significant cardiac or pulmonary disease, chronic or recurrent renal or urinary tract disease, liver disease other than CHB, endocrine disorder, autoimmune disorder, diabetes mellitus requiring treatment with insulin or hypoglycemic agents, neuromuscular, musculoskeletal, or mucocutaneous conditions requiring frequent treatment, seizure disorders requiring treatment, ongoing infection or other medical conditions requiring frequent medical management or pharmacologic or surgical treatment that in the opinion of the Investigator or the Sponsor makes the subject unsuitable for study participation
7. History of HCC

8. History of malignancy other than HCC unless the subject's malignancy has been in complete remission off chemotherapy and without additional medical or surgical interventions during the 3 years before Screening
9. Poorly controlled or unstable hypertension; or sustained systolic blood pressure (BP) ≥ 160 mmHg or < 90 mmHg, or diastolic BP > 95 mmHg or < 50 mmHg at Screening
10. History or presence of electrocardiogram (ECG) abnormalities deemed clinically significant including:
 - a. Personal or family history of prolonged QT syndrome or family history of sudden death
 - b. QTcF > 450 msec (males) or > 470 msec (females) or < 300 msec at Screening or Day 1 visit
 - c. ECG with QRS and/or T-wave judged to be unfavorable for a consistently accurate QT measurement as judged by the Investigator at Screening

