7.8.4 Electrocardiograms

A standard 12-lead ECG will be obtained as specified in the Schedule of Assessments ([Appendix 1](#)). Prior to the conduct of the 12-lead ECG, subjects should rest in a supine position for 10 mins. ECGs should be conducted in accordance with local practice and equipment. The ECG assessment will include interpretation of the tracings (eg, rhythm, presence of arrhythmia or conduction defects, morphology, any evidence of myocardial infarction, or ST segment, T-wave, and Uwave abnormalities). The Investigator or a physician Sub-Investigator is responsible for reviewing and overreading the ECG interpretation, for assessing whether the ECG machine interpretation findings are accurate, appropriate,

normal or abnormal, and for providing corrected interpretations as appropriate. In addition, any abnormal ECGs will be assessed for clinical significance.

Additional ECGs may be obtained if clinically indicated and will be obtained if abnormal and clinically significant or thought to be an error (eg, lead placement error, movement artifact, etc.). Any additional relevant data obtained by the Investigator during the course of this study will be recorded in the subject's source documentation. The Investigator or a physician Sub-Investigator will review all ECGs, evaluate the results, and sign/date the tracing or report. For any ECG abnormality that the Investigator considers clinically significant, the Investigator will:

- Repeat the ECG;
- Obtain follow-up ECG(s) if any significant abnormalities are detected after study drug administration to document resolution and as clinically indicated;
- Record as an AE any ECG abnormality that: (1) is confirmed and the Investigator considers clinically significant; (2) requires a subject to be discontinued from the study; or (3) the abnormality requires a subject to receive treatment. ([Section 8](#)).

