10.4.4 Analysis of Safety Endpoints

The safety parameters to be assessed are described in [Section 7.8](#) Displays for safety results will utilize descriptive statistics. No formal hypothesis testing of safety data is planned.

Adverse events will be coded using the Medical Dictionary for Regulatory Activities (MedDRA). Incidence of each body system and preferred term will be tabulated for each treatment group. Treatment-emergent adverse events (TEAE) are defined as those reported on or after the first dose of study drug through 28 days from the last dose of study drug. Summaries will include all TEAEs, TEAEs

considered related to study treatment by investigators, Graded TEAEs, and SAEs. All AEs, emergent or non-emergent, will be listed by subject. Any TEAEs leading to premature discontinuation from the study intervention and serious TEAEs will be presented by listing.

Clinical laboratory results will be summarized descriptively by treatment group including values, changes from Baseline, and incidence of laboratory abnormalities. Laboratory results will be listed for each subject.

Vital sign data and ECG findings reported at each visit will be displayed by treatment, using descriptive statistics for observed and change from Baseline values.

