6.2. Changes From Protocol-Specified Efficacy Analyses

Since the study is terminated early, the analyses for the key secondary and other secondary endpoints specified in the protocol are not performed.

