7.3. Vital Signs

Descriptive statistics will be provided by treatment group for vital signs including heart rate, respiration rate, blood pressure, and body temperature as follows:

- Baseline value
- Values at each postbaseline time visit

- Change from Baseline at each postbaseline visit

A baseline value will be defined as the last available value collected on or prior to the date/time of first dose of study drug. Change from Baseline to a postbaseline visit will be calculated for any postbaseline visit.

In the case of multiple values in an analysis window, data will be selected for analysis as described in Section 3.6.3.

A by-subject listing of vital signs (systolic and diastolic blood pressure [mmHg], respiration rate [breaths/min], heart rate [bpm] and body temperature) will be provided by subject ID number and visit in chronological order.

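### SAP 7.5 omits, without saying so, the by-arm ECG change-from-Baseline summaries of protocol 10.4.4; interval shifts that leave the Investigator's category unchanged reach no by-arm summary

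*Combined protocol and SAP*

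**What the plan says.** Protocol 10.4.4 covers vital signs and ECG in one sentence: "Vital sign data and ECG findings reported at each visit will be displayed by treatment, using descriptive statistics for observed and change from Baseline values".

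The SAP splits the two. SAP 7.3 gives vital signs a baseline value, a value at each later visit, and "Change from Baseline at each postbaseline visit". SAP 7.5 gives ECG a different display: "A shift table of the Investigators' assessment of ECG results at each visit compared with baseline values will be presented by treatment group". Its categories are normal, abnormal but not clinically significant, abnormal and clinically significant, and missing or not done. It adds one more output: "A by-subject listing for ECG assessment results will be provided by subject ID number and visit in chronological order". No SAP section plans a by-arm summary of PR, QRS, QTc or heart rate taken from the ECG.

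The only SAP section on departures from the protocol, 6.2, concerns efficacy. It says that "the analyses for the key secondary and other secondary endpoints specified in the protocol are not performed". SAP 1 adds, in general terms, that analyses are limited to key safety and efficacy endpoints because development was stopped on 01 September 2021.

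**The concern.** The protocol asks for a summary that shows how far ECG values moved in each arm. The SAP offers one that shows only whether a reader's judgement changed category. A category discards size: if an interval lengthens moderately in most treated subjects and each tracing is still read as normal, the shift table shows nothing.

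Safety and tolerability is a primary objective, and the comparison with placebo is what allows a modest interval effect to be told apart from drift. The omission is also undeclared. A reader of the synoptic CSR could not tell whether the numeric display was dropped on purpose, dropped because the values were never captured, or overlooked.

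**Working it through.** The plan contains no ECG figure to reproduce. It states no SD, effect size, alpha or power, and protocol 10.2 says the sample size has no statistical basis. The check is therefore a comparison of texts, followed by an illustration on assumed inputs.

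**1. Side by side**

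| Item | Protocol 10.4.4 | SAP |
|---|---|---|
| Vital signs | observed and change from Baseline, by visit and arm | kept (7.3) |
| ECG | observed and change from Baseline, by visit and arm | Investigator-category shift table by arm, plus listing (7.5) |
| Statement that the ECG display changed | not applicable | none (6.2 covers efficacy; 1 is general) |

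**2. Is a numeric display the right reading of the protocol?** It is an inference, but a reasonable one. A change from Baseline, summarised by descriptive statistics in the same sentence as vital signs, is naturally numeric. Interval values are read at least at entry, because exclusion criterion 10b is "QTcF > 450 msec (males) or > 470 msec (females) or < 300 msec at Screening or Day 1 visit". Protocol Appendix 2 also grades PR and QTc, which needs a measured interval.

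**3. What still reaches a by-arm table?** A change that alters the Investigator's category enters the shift table. Under protocol 7.8.4, an abnormality that is confirmed and judged clinically significant is recorded as an AE, and SAP 7.1.6 tabulates treatment-emergent AEs by preferred term, grade and arm. SAP 7.3 summarises heart rate numerically as a vital sign. What remains uncovered is a shift in PR, QRS or QTc that does not move the Investigator's category.

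**4. Illustration (all ECG inputs assumed)**

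Half-width of the 95% CI for a difference in mean change = t(0.975, n1+n2−2) × SD × √(1/n1 + 1/n2). The planned numbers are 30 v 10 per cohort, so 60 v 20 if the cohorts are pooled. The assumed SD of QTcF change is 15 ms (range 10 to 20).

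- 30 v 10: 2.024 × 15 × √(1/30 + 1/10) = 2.024 × 15 × 0.365 = 11.1 ms (7.4 to 14.8).
- 60 v 20: 1.991 × 15 × √(1/60 + 1/20) = 1.991 × 15 × 0.258 = 7.7 ms (5.1 to 10.3).

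For contrast, assume QTcF is normal with mean 410 and SD 18 ms, and shift the mean by 10 ms. The share above 450 ms goes from P(Z > 40/18 = 2.22) = 1.3% to P(Z > 30/18 = 1.67) = 4.8%. In 60 subjects that is 0.8 against 2.9.

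This uses 450 ms as a stand-in for the Investigator's judgement, which the SAP does not define that way. It also ignores the truncation that criterion 10b imposes. It shows why a category is less sensitive than a mean; it does not estimate what this trial would find.

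**The case against.** A reader might infer that a drug effect on QTcF would go unreported. The documents do not support that. Substantial effects have the by-arm routes set out in the working, and SAP 7.5 gives abnormal but not clinically significant readings a category of their own.

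The case against goes further:

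- **Numeric intervals are not promised by name.** Protocol 10.4.4 speaks of ECG findings, and SAP 3.6.3 uses that term for a normal/abnormal reading. Protocol 7.8.4 says "The ECG assessment will include interpretation of the tracings" and names no interval variable on study. Protocol 7.8 allows some evaluations to stay off the case report form, and the eCRF is not available here. This stands: whether interval values are in the database cannot be settled from the documents, so the fix must be conditional.
- **The SAP was shortened deliberately.** SAP 1 limits the analyses after termination, the report is a synoptic one, and protocol 10.1 leaves detailed methods to the SAP. ECG is not named in the primary safety endpoint (protocol 3.2.1). That could justify dropping the display. It does not say that the display was dropped, and the numeric vital-sign summaries survived the same shortening.
- **Precision is poor.** The per-cohort half-width of 11.1 ms at planned numbers already exceeds the 10 ms example. This also stands. A summary with a wide interval is still more informative than none, but it should not be presented as able to exclude a moderate effect.
- **Availability is unknown.** ECGs were scheduled at Weeks 12 to 72, but the documents do not say how many subjects reached those visits before termination.

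**Conclusion.** The discrepancy is real and undeclared: protocol 10.4.4 plans by-arm observed and change-from-Baseline ECG summaries, SAP 7.5 does not provide them, and SAP 7.3 keeps the matching display for vital signs. The consequence is limited to interval shifts that leave the Investigator's category unchanged.

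The size of any missed effect cannot be derived from the documents. The millisecond figures rest wholly on assumed SDs and an assumed baseline distribution, and precision would be lower again after early termination. The conclusion also assumes that the protocol's wording is meant numerically for ECG, as it plainly is for vital signs. This is a low-cost improvement to the reporting of a primary safety objective; it is not evidence of a hidden safety signal.

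**What to change.** Add to SAP 7.5, next to the shift table, by-arm and by-visit descriptive statistics of observed values and change from Baseline for the ECG values held in the database: heart rate, PR, QRS and QTcF. The ECG visit windows in SAP Tables 3-2 and 3-4 can be used as they are.

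If categorical QTc counts are added as well, state the correction formula for each. Appendix 2 grades QTc by Bazett's formula, while criterion 10b uses QTcF, so the Appendix 2 grades should not be applied to QTcF values without saying so.

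If intervals were not captured, add a sentence to the synoptic CSR recording the departure from protocol 10.4.4 and its reason.

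The cost is one or two extra tables, and possibly the transfer of interval values that exist only on tracings. The documentation route costs one sentence.

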9. SOFTWARE

SAS[®] Software Version 9.4. SAS Institute Inc., Cary, NC, USA.

